Prior research indicates that college students are at high risk for engaging in unintentional and intentional tanning behaviors that dramatically increase their UVR exposure and that they use inadequate sun protection strategies when they are outdoors.^{6,7} However, few studies have examined novel strategies to improve college students' use of sun protection and decrease their intentional tanning behaviors.^{8,9} Prior studies have shown that traditional risk communication strategies do not effectively change college students' health behaviors.^{10,11} It is possible that college students require more novel forms of risk information in order to motivate behavior change, and that these new forms of risk information should be grounded in established theoretical models. In the current study, we will test several theoretically-driven risk communication strategies that aim to improve college students' engagement in skin cancer prevention behaviors, including sun protection behaviors (sunscreen, protective clothing, shade, peak UVR hours avoidance) and tanning behaviors (indoor, outdoor, unintentional).

Based on prior literature,¹² we anticipate low levels of distress regarding *MCIR* feedback. In the current study, we will test several theoretically-driven risk communication strategies that aim to improve college students' engagement in skin cancer prevention behaviors, including sun protection behaviors (sunscreen, protective clothing, shade, peak UVR hours avoidance) and tanning behaviors (indoor, outdoor, unintentional).

Purpose and Objectives

The purpose of this study is to test the feasibility of providing young people with skin cancer prevention education and/or personalized feedback on their risk for skin cancer using novel methods of communicating this risk. In addition, we will examine the effects that the education and risk feedback have on individuals' reported sun protection and tanning behaviors.

Study Population

Age of Participants: 18+

Sample Size:

At Utah: 300

All Centers: 300

Inclusion Criteria:

Individual is enrolled in courses at the University of Utah

And

Individual reports having had at least 1 sunburn in past year

And/or

Individual reports having intentionally indoor or outdoor tanned at least 1 time in the past year

And/or

Individual reports using sunscreen plus 1 or more of the following behaviors never/rarely/sometimes in the past month: 1) Protective clothing items, 2) Shade when outdoors

Exclusion Criteria:

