Descriptive statistics (number, percent for categorical variables and mean, standard deviation for quantitative variables) were calculated for demographic characteristics and participant's sun protection and tanning outcomes. For inferential statistical analyses, missing data was handled via multiple imputation, which ensures valid inference under missingness-at-random (data values independent of missingness pattern, conditional on the observed data), the most general data-centered missing data assumption. Twenty complete data sets were generated and all statistical analyses were based on these, with pooling via Rubin's rules. The primary outcomes of interest include sun protection and tanning. In order to estimate changes in outcomes over time overall and compare changes over time between the four intervention groups, generalized estimating equations (GEE) were used to account for repeated measures within individuals. Season of participation (fall versus spring) was considered an important factor for the primary outcomes, so it was included as an adjustment factor in all models and outcomes were also examined within each season separately.

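### Twenty imputations give valid inference but leave avoidable seed-to-seed noise in every inferential result; at least 100 would cut that noise by a little more than half, for computing time only (minor)

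*Combined protocol and SAP*

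**What the plan says.** The section on statistical methods, data analysis and interpretation states that "missing data was handled via multiple imputation" for the inferential analyses, justified as a method "which ensures valid inference under missingness-at-random". It then says "Twenty complete data sets were generated and all statistical analyses were based on these", "with pooling via Rubin's rules".

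The same 20 data sets therefore serve both primary outcome domains (sun protection and tanning), the overall changes over time, the comparison of the four groups by GEE, and the separate looks at fall and spring. The planned sample is 300.

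The section gives no amount of missing data, fraction of missing information, random seed, Monte Carlo error, significance level or reason for choosing 20. It is written in the past tense.

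**The concern.** Multiple imputation is itself a random procedure. If the same data are imputed again with another seed, the pooled estimate, its standard error and the p-value all move. Relative efficiency, the usual argument for a small number of imputations, measures only the average loss of precision. It does not show how far a single reported p-value can move.

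With several outcomes and comparisons, read both pooled and by season, some results may well lie close to whatever threshold is used. For those, the seed can decide whether a result is called significant. A reader cannot judge how likely that is, because neither the seed nor the Monte Carlo error is reported. More imputations reduce this noise without touching the design, the GEE model or the missing-at-random assumption.

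**Working it through.** **Inputs from the documents.** Number of imputations m = 20; Rubin's rules; N = 300. The plan gives nothing from which 20 could be derived, so there is no figure to reproduce.

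**Assumptions, because the documents are silent.** Fraction of missing information (FMI) from 0.05 to 0.50; two-sided alpha 0.05; 80% power where power is needed.

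**Model of the seed noise.** Scale the total variance with unlimited imputations to 1, so the between-imputation variance is B = FMI and the within-imputation variance is W = 1 - FMI. For one imputation run:

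- pooled estimate = unlimited-imputation estimate + N(0, B/m)
- estimated between-imputation variance b = B × chi-square(m - 1)/(m - 1)
- total variance T = W + (1 + 1/m) b
- p-value from t with Rubin's degrees of freedom, (m - 1)[1 + W/((1 + 1/m) b)]²

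W is held fixed and the complete-data degrees of freedom are taken as large, so the results are approximate.

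**Average precision.** Relative efficiency is 1/(1 + FMI/m). At m = 20 this is 0.995, 0.985 and 0.976 for FMI 0.1, 0.3 and 0.5.

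**Monte Carlo error of the estimate relative to its standard error** is sqrt(FMI/m). At FMI 0.3 it is sqrt(0.3/20) = 0.122 with 20 imputations and sqrt(0.3/100) = 0.055 with 100. The ratio is sqrt(20/100) = 0.447, a reduction of 55%. Holding this error to 5% needs m = FMI/0.05²: 20 at FMI 0.05, 40 at 0.1, 120 at 0.3 and 200 at 0.5.

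**Rough check by hand** (FMI 0.3, m = 20, unlimited-imputation p = 0.05). Noise in the estimate alone moves z over 1.96 ± 1.96 × 0.122, that is 1.72 to 2.20, or p from about 0.085 down to 0.028. Noise in the standard error widens this further.

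**Simulated central 95% range of reported p** for a result whose unlimited-imputation p is 0.05, with the standard deviation (SD) of p over seeds (400,000 seeds per cell):

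| FMI | 20 imputations | SD | 100 imputations | SD |
|---|---|---|---|---|
| 0.05 | 0.039-0.064 | 0.006 | 0.045-0.056 | 0.003 |
| 0.10 | 0.035-0.072 | 0.009 | 0.043-0.059 | 0.004 |
| 0.30 | 0.024-0.101 | 0.020 | 0.036-0.068 | 0.008 |
| 0.50 | 0.017-0.130 | 0.029 | 0.032-0.078 | 0.012 |

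If the unlimited-imputation p is 0.04, the share of seeds reporting p of 0.05 or more falls from 13% to 0.4% at FMI 0.1, and from 33% to 10% at FMI 0.3, on going from 20 to 100 imputations.

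**Averaged over whole trials, not only near-threshold results** (2,000,000 trials per cell, two seeds each):

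| FMI | m | Type I error | Seeds disagree, null | Power (nominal 80%) | Seeds disagree, 80% power |
|---|---|---|---|---|---|
| 0.1 | 20 | 5.0% | 1.0% | 79.8% | 2.5% |
| 0.1 | 100 | 5.0% | 0.5% | 80.0% | 1.1% |
| 0.3 | 20 | 5.0% | 2.1% | 79.0% | 5.2% |
| 0.3 | 100 | 5.0% | 0.9% | 79.8% | 2.2% |
| 0.5 | 20 | 5.0% | 3.0% | 78.0% | 7.8% |
| 0.5 | 100 | 5.0% | 1.3% | 79.6% | 3.2% |

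**The case against.** The strongest reply is that nothing is wrong with the inference. Rubin's rules carry the (1 + 1/m) term and a t reference, so 20 imputations are already allowed for: type I error is 5% and the power lost is at most about 2 points. That stands. A reader might infer that 20 imputations make the p-values invalid or inflate false positives; the calculation shows they do not.

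Secondly, the size depends on an unknown. The study is short, with up to three visits about four weeks apart and the last possibly remote, so missing information could be low. At 5% missing information, 20 imputations already meet the 5% Monte Carlo target. The widest ranges also describe results chosen to sit at the threshold. This stands too: nothing in the documents makes 30% the central case, and alpha and power are assumptions made here.

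Thirdly, it is tempting to say that 20 was fixed regardless of how much was missing. The text gives no reason for the number, and an absent reason does not show that missingness was ignored.

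Finally, because the text describes completed work, a rerun could create a choice between two sets of p-values. That governs how the change should be made. It is not a reason to keep 20.

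None of this supplies a reason to prefer 20 over a larger number.

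**Conclusion.** The point holds as a minor, free improvement in reproducibility. With 20 imputations the run-to-run noise is modest at about 10% missing information or less (SD of p up to about 0.009 for a result at 0.05). It is substantial at 30% or more (SD about 0.02 or higher). Moving to 100 at 30% missing information lowers two-seed disagreement from about 5% to about 2% of trials at 80% power. It also recovers about 0.7 to 0.8 points of power, or about 1.7 points at 50% missing information.

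Two stronger statements are not supported. The first is that this trial's conclusions do depend on the seed: that would need the fraction of missing information and the actual p-values, and the documents give neither. The second is that 100 imputations would largely remove the noise: they cut it by about 55-60%.

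**What to change.** In the statistical methods section, replace twenty with at least 100 imputations generated from a recorded seed. Add one sentence: the Monte Carlo error of each primary estimate will be reported, and imputations will be added if it exceeds about 5% of that estimate's standard error (about 120 in total at 30% missing information, 200 at 50%). Report the amount of missing data and the estimated fraction of missing information alongside.

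If the 20-imputation analysis has already been run, fix the new number and seed before rerunning, and report both sets of results whatever they show.

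The cost is computing time only, which should be small for 300 people at up to three visits (not timed here). The sample size, GEE model and missing-at-random assumption are unchanged.

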1. Participants will be provided all of the required information about the study via the consent document. 2. We will give participants this information in a language they understand (English). We will use language that is simplified and appropriate for potential participants to understand. Participants that do not speak/read or write in English will be excluded from the study. 3. Participants will be given an opportunity to ask questions before they consent and to ensure that the individual has had enough time to review the consent form to before they sign the consent. The study staff will review the consent form with potential participants and be available to potential participants to ask any questions they may have. 4. Participants will be given time to review the consent and consider being in the study. If the participant wants to take more time to consider whether they want to participate in the study, study staff will schedule another time to complete the consent and visit 1 procedures with them. 5. We will use clear and easy to understand language in the consent document and will not include exculpatory language. 6. Consent will be documented by obtaining a signature from the participant, and study staff will keep the signed document in the research record. 7. Participants will receive a copy of their signed consent documents via email, mail, fax, or in person.

Procedures:

Arm 1: Skin Cancer Education Only

Screening: Participants will have the option to complete an online or text based screening form. Study staff may contact participants who screen to be eligible via phone, text, or email. Study staff will screen potential participants who do not complete the screening form on their own for eligibility. Participants will be contacted by phone, text, or email (starting with the method they indicated would be best to reach them) to schedule their first study visit.

Enrollment

Visit 1: All participants who consent to participate will be asked to participate in up to 3 study visits approximately 4 weeks apart. At visit 1, all participants will be asked to complete informed consent procedures and a baseline questionnaire via computer (e.g., using

Qualtrics) or paper. Participants will be randomized to receive education only, or varying combinations of the intervention components.

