Visit 2: At visit 2 participants will receive education on the importance of skin cancer prevention behaviors (e.g., sunscreen, protective clothing) and avoiding tanning and sunburns. Participants will be provided with their personalized risk feedback based on a summary of their personalized UV photo and a summary of their MC1R genetic testing results. All information will be delivered at this visit on a computer screen and additionally given to participants as a handout they can take home to review. When participants view their results on the computer screen, eye tracking will be used to assess participant response. Prior to viewing results, eye tracking equipment set up at the computer station will be calibrated. We will then put up their results on the screen and the imotion system will then track their

pupillary movement, facial expression, and galvanic skin response (physiological arousal). Participants will be allowed as much time as they would like to review their results. Following this, participants will complete a post assessment. The imagery resulting will be kept on file in a password protected computer. Participants will receive paper copies of all of the relevant information to take home with them.

Visit 3: Visit 3 may be conducted remotely. At visit 3, participants will complete a follow-up assessment. Participants who have clinical questions about melanoma or concerns about their family history will be referred to speak with a genetic counselor or be referred to HCI's Family Cancer Assessment Clinic (FCAC) for further information and information on CLIA testing.

Follow-up interview: A random sample of the participant population will be contacted to participate in a follow-up interview with study staff to answer questions about their experience participating in the RISE-UP study.

Procedures performed for research purposes only:

Statistical Methods, Data Analysis and Interpretation

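### Season is the only adjustment named for the GEE comparison of changes; if the visit 1 outcome enters only as a response, the between-arm contrasts are valid but usually less precise than they could be

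*Combined protocol and SAP*

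**What the plan says.** The section on Statistical Methods, Data Analysis and Interpretation states: "The primary outcomes of interest include sun protection and tanning". To estimate change overall and to "compare changes over time between the four intervention groups, generalized estimating equations (GEE) were used to account for repeated measures within individuals". Season (fall or spring) was thought important, "so it was included as an adjustment factor in all models and outcomes were also examined within each season separately". No other covariate is named. The section does not say whether the visit 1 value of the outcome is a response, a covariate, or a response with one mean shared by the arms. It gives no link and no working correlation. Missing data were handled with twenty imputed data sets; the imputation model is not described. The section is in the past tense.

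The data for an adjustment exist. Under Procedures, in the Visit 1 description of each arm, "all participants will be asked to complete informed consent procedures and a baseline questionnaire via computer" or on paper, and the personalised feedback comes only at visit 2. Later, "At visit 3, participants will complete a follow-up assessment". The sample size is given as "All Centers: 300", with no derivation.

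**The concern.** In a randomised trial the arms share one expected visit 1 mean. A model that gives each arm its own free visit 1 mean does not use that fact. It subtracts the whole baseline difference between arms, chance noise included, where an adjusted analysis subtracts only the part that predicts follow-up.

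The effect is on precision: the confidence intervals for the between-arm contrasts on the primary outcomes may be wider than the collected data allow. Four arms share 300 participants, and the analyses by season divide them again. The same relative loss leaves less power there.

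**Working it through.** **Inputs from the documents.** Four randomised arms, 300 participants, a visit 1 questionnaire in every arm, follow-up at visit 3, season in all models, missing values imputed. There is no stated power or precision figure to reproduce.

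**Assumed, because the documents do not give them.** Equal allocation (300/4 = 75 per arm); about 37 per arm in one season; a continuous outcome with identity link; baseline and follow-up SDs s0 and s1; correlation ρ; observed fraction of follow-up f; two-sided 5% and 80% power.

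**Step 1: which contrast the model gives.** Season is constant within a participant, so a season main effect cancels from follow-up minus visit 1. With complete data and free group-by-visit means, the contrast is therefore the raw difference in mean change, and season adds no precision to it. In simulation (4 arms of 75, three visits, 3,000 runs at each of three correlations) the two agreed to rounding error.

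**Step 2: variance per participant, common slope and variances across arms.**
- Change: s0² + s1² − 2ρ·s0·s1
- Adjusted for visit 1: s1²(1 − ρ²)
- Saving: (s0 − ρ·s1)², which is never negative
- With equal SDs of 1: 2(1 − ρ) against 1 − ρ², a ratio of (1 + ρ)/2

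**Step 3: incomplete follow-up.** If a fraction f is observed and the rest is imputed from baseline, the adjusted variance is (1 − ρ²)/f. The change variance is (1 − ρ²)/f + (1 − ρ)². Missing data inflate the part common to both and leave the saving unchanged, so the relative gain shrinks.

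**Step 4: narrowed baseline.** If eligibility cuts off the top of a normal baseline score and leaves a fraction v of its variance, the ratio is (1 − ρ²)/[(1 − ρ²) + (1 − ρ)²·v], with ρ taken before selection. Here v = 0.71 when the top 10% is removed and 0.36 when the top 50% is removed.

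Variance ratio, adjusted to change:

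| Assumption | ρ = 0.3 | ρ = 0.5 | ρ = 0.7 |
|---|---|---|---|
| Equal SDs, complete follow-up | 0.91/1.40 = 0.65 | 0.75/1.00 = 0.75 | 0.51/0.60 = 0.85 |
| Equal SDs, f = 0.8 | 1.1375/1.6275 = 0.70 | 0.9375/1.1875 = 0.79 | 0.6375/0.7275 = 0.88 |
| Follow-up SD 0.8 × baseline, complete | 0.50 | 0.57 | 0.63 |
| Follow-up SD 1.4 × baseline, complete | 0.84 | 0.94 | 1.00 |
| Top 10% of baseline cut off, complete | 0.72 | 0.81 | 0.89 |
| Top 50% of baseline cut off, complete | 0.84 | 0.89 | 0.94 |

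A simulation of the second row with 20 imputations (1,500 trials, 75 per arm) gave 0.74 / 0.80 / 0.88.

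**Step 5: unequal slopes.** A single pooled slope can lose. With equal SDs and correlations of 0.8, 0.8, 0.3 and 0.3 in arms 1 to 4, the pooled slope is 0.55. For arms 1 and 2 the adjusted variance is 1 − 2(0.55)(0.8) + 0.55² = 0.4225, against 0.40 for change: a ratio of 1.06. Baseline-by-arm terms give 0.36/0.40 = 0.90.

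**Step 6: detectable pairwise difference**, equal SDs, in SD units: (1.960 + 0.842)·√(2 × variance/n).
- 75 per arm, complete follow-up: 0.541 to 0.436 (ρ = 0.3), 0.457 to 0.396 (ρ = 0.5), 0.354 to 0.327 (ρ = 0.7).
- 75 per arm, f = 0.8, ρ = 0.5: 0.499 to 0.443.
- 37 per arm in one season, complete, ρ = 0.5: 0.651 to 0.564.

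**Step 7: bias, and the two forms of adjustment.** In the simulation of step 1 every estimator averaged within 0.004 of the true value of zero. Empirical SDs for change, visit 1 covariate and common visit 1 mean were 0.195 / 0.158 / 0.158 at ρ = 0.3, 0.168 / 0.145 / 0.144 at 0.5 and 0.127 / 0.117 / 0.116 at 0.7. The two forms of adjustment are practically equivalent here.

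**The case against.** The best reply is that no error is shown. The model is unspecified, and repeated-measures GEE is valid for both stated aims. If the sponsor used a common visit 1 mean with a non-independence working correlation, most of the gain is already there. This stands, and it is why the point is conditional. It does not dispose of it: the section names season and is silent on the visit 1 outcome, and adding that value is a definite change using data in hand.

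The size is also open. Correlation, SDs, allocation and dropout are all assumed, and the table with step 5 runs from a halved variance to a small loss. The outcome scale is unstated. One eligibility route is worded in frequency categories ("Individual reports using sunscreen plus 1 or more of the following behaviors never/rarely/sometimes in the past month"), so the outcomes may not be continuous. That route, and those based on sunburn and tanning, select on related behaviours and may narrow the baseline spread. All of this stands; the figures are illustrations.

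Finally, feasibility is named first under Purpose and Objectives, and the behavioural aim follows with "In addition, we will examine the effects that the education and risk feedback have on" reported behaviours. A new contrast may also be post hoc. Both lower the priority. But the statistical section itself makes the behaviours the primary outcomes.

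A reader might infer that the reported comparison is biased, or that the sponsor is known to have ignored baseline. The documents support neither. Randomisation makes the difference in mean change valid, and naming one factor in all models does not exclude others.

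**Conclusion.** The point holds as a conditional matter of efficiency, worth considering, with medium confidence. It requires an identity link and a visit 1 value that enters only as a response with arm-specific means. Under equal SDs and a common slope, adjustment would then remove about 15% to 35% of the contrast's variance with complete follow-up, and about 12% to 30% with an assumed 80% observed, for correlations from 0.7 down to 0.3. The gain shrinks where eligibility has narrowed the baseline, and vanishes where the follow-up SD is so large that ρ·s1 is close to s0. No figure is offered for binary or count outcomes. If baseline was in fact adjusted for, nothing was lost and only the description is incomplete.

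**What to change.** Keep season, and keep the present GEE for overall change over time. State the mean model, link and working correlation. For the between-group contrasts, use one of two forms, with robust standard errors:

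1. Follow-up as the response and the visit 1 value of the same outcome as a covariate. If slopes may differ between arms, add baseline-by-arm terms with baseline centred at its overall mean.
2. Visit 1 kept as a response with one mean common to the randomised arms, and a non-independence working correlation. This retains a single GEE.

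The imputation model must contain the visit 1 value and arm, and their interaction if by-arm slopes are fitted; otherwise imputed values pull the slopes together. With a logit link, standardise the adjusted model so that the estimand stays marginal.

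If the analyses are complete, report this as an additional analysis labelled post hoc, beside the existing result. If baseline was already adjusted for, one sentence saying so is enough.

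No new data are needed. The cost is one further model per outcome, a standardisation step for any binary outcome, and possibly a re-run of the imputation. By-arm slopes cost a little precision when slopes are in fact equal: a simulated ratio of 0.77 against 0.75 at 37 per arm and correlation 0.5.
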